#### 4.6.2 Sources for overall lesion response

The tumor endpoints derivation is based on the sequence of overall lesion responses at each assessment/time point. However, the overall lesion response at a given assessment/time point will be provided from different sources as illustrated in [Table 4-3](#).

**Table 4-3 Sources for overall lesion response**

Source 1	Investigator (local radiology) reported overall lesion response
Source 2	Calculated overall lesion response based on raw (i.e. individual lesion) measurements from Investigator (local radiology)
Source 3	BIRC (Blinded Independent review committee) reported overall lesion response

In this study, Source 1 will be used for the primary endpoint derivation and other secondary endpoint calculations based on investigator assessment (ORR, DCR, DOR, TTR and PFS) and Source 2 will be listed against Source 1 and discrepancies between calculated and reported responses assigned by investigator will be identified. Source 3 will be used to calculate ORR, DCR, DOR, TTR and PFS by BIRC.

#### 4.6.3 Kaplan-Meier estimates

To analyze time to event variables (DOR, TTR, OS and PFS) an estimate of the survival function will be constructed using *Kaplan-Meier (product-limit) method* as implemented in PROC LIFETEST with METHOD=KM option (see example below). The median time to event and estimated event rates at different time points will be estimated, along with associated 90% or 95% two-sided CIs derived based on the complementary log-log

transfonnation. This will be conducted via the SAS procedure LIFETEST. The TIME statement will include a variable with survival times (*survtllle* in the example below) and a (iight) censoling variable (*ensor* in the example below) with a valtle of 1, representing censoring (example code below for constmction of 90% CIs):

```
PROC LIFETEST data = dataset
  METHOD = KM
  ALPHA = 0.1
  ALPHAQT = 0 .1
  CONFTYPE=LOGLOG ;
TIME survtime*ensor(1) ;
RUN;
```

*/\* survtime* represents variable containing event/censor times;  
*ensor* represents censoiing variable (1 = censored, 0 = event); \*/

Kaplan-Meier sUtv iv aJ and failure fmcion estimates from this procedure will be used to construct the Kaplan-Meier figures

Median smvival will be obtained along with 2-sided 90% or 95% CIs calculated from PROC LIFETEST output using the method ofBrookmeyer & Crowley, 1982.

Kaplan-Meier estimates with 2-sided 90% or 95% Cis at sp ecific tim e points will be summarized. The time points can be expressed in weeks or in months depending on the time- to-event variable. The Cis will be constmcted using Greenwood's foImula [Collet , 1994 , p.23] for the standard enor of the Kaplan-Meier estimate.

The Kaplan-Meier graphs will be constncted usingSAS software.

#### 4.6.4 Confidence interval andp-value for response rate

ORR will be sununalized in telms of percentage rates with 90% and 95% Cis. An exact binomial confidence interval (implemented using SAS procedure FREQ with EXACT statement for one-way tables) will be calculated ([Clopper and Pearson 1934](#)).

SAS procedlu.e FREQ will be used to estimate ttle proportion of responders (binaly outcome= 1 or "Yes"), along with the associated 90% or 95% (=100 x (1 - *two-sided alpha level*)) two-sided Pearson-Clopper CI and exact one-sided p-value for ttle hypothesis test of the *null proporrion* (0.35). These estiniates are obtained as follows:

```
proc freq data= dataset ;
  table binary event I
    binomial(
      p = null proportion
      level = "Yes ")
    alpha= two-sided alpha level ;
  exact binomial ;
```

When there are no responders, SAS does not produce a CI by default. To obtain a CI in this situation, PROC FREQ is used as specified above except changing **level**="No". From the

results of this modified procedure, the values in percent of the LCL and UCL of a 0% response rate are calculated as follows:

$$\text{LCLLEVEL}=\text{"Yes"} (\%) = 100\% \cdot \text{UCLLEVEL}=\text{"No"} (\%)$$

$$\text{UCLLEVEL}=\text{"Yes"} (\%) = 100\% \cdot \text{LCLLEVEL}=\text{"No"} (\%)$$

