10.4.2 Statistical hypothesis, model, and method of analysis

The primary analysis will be performed on the FAS.

The study targets an ORR of 50%. A response rate of 35% or less is considered as insufficient level of activity for the proposed patient population. Therefore, a null hypothesis of $ORR \leq 35\%$ vs. an alternative hypothesis of $ORR > 35\%$ will be tested using a one-sided test with alpha of 0.05 based on a Simon's optimal two-stage design ([Simon 1989](#)). If 45 or more responses are seen in 105 total patients (estimated ORR of 42.9%), then the null hypothesis will be rejected and the trial declared positive.

Stage 1 will enroll 43 patients. If the study is terminated early at the end of Stage 1 (16 or fewer responses among 43 patients enrolled to Stage 1), then the study will be considered to have failed to reject the null hypothesis. See [Section 10.7](#) for further details of the stopping

criteria for futility. Stage 2 will include an additional 62 patients. The primary analysis will occur when all 105 patients have completed 6 cycles of treatment or discontinued treatment earlier.

The ORR will be estimated and the 90% exact confidence interval (CI) will be provided. The uniformly minimum variance unbiased estimator (UMVUE) and the 90% two-stage CI (Atkinson and Brown 1985) will also be presented.

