10.8 Sample size calculation

Based on [Simon's \(1989\)](#) optimal two-stage design, if the true ORR is 50% (under the alternative hypothesis), approximately 105 total patients are required to reject the null hypothesis of $ORR \leq 35\%$ with a one-sided alpha of 0.05 and 90% power. If at least 17 confirmed responses are observed among 43 patients enrolled into Stage 1, an additional 62 patients will be enrolled into Stage 2. If 45 or more confirmed responses are observed among 105 total patients, the trial will be declared positive.

The operating characteristics of the design are described in [Table 10-1](#).

Table 10-1 Operating characteristics of Simon's optimal two-stage design

	True ORR			
	35% (null hypothesis)	40%	45%	50% (alternative hypothesis)
Probability stop for futility at Stage 1 (16 or fewer responses out of 43 patients enrolled at Stage 1)	0.683	0.418	0.192	0.063
Probability trial is success (45 or more responses out of 105 total patients)	0.049	0.268	0.642	0.900

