## 2 Statistical methods

This section and its subsections will be imported to section 9.7 of the CSR after the analyses have been conducted. This section of the RAP follows the CSR template structure of Section 9.7 as of the release date of this document.

The text will be changed to the past tense when imported into the CSR; references to Section 4, where additional details are provided for programming implementation, may be removed in the CSR.

In what follows, study drng refers to LDK378/Cerit:inib.

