### **2.7.2 Statistical hypothesis model and method of analysis**

The primary efficacy analysis will be performed on the FAS.

The study targets an ORR of 50%. A response rate of 35% or less is considered as insufficient level of activity for the proposed patient population. Therefore,

$H_0: \text{ORR} \leq 35\%$  will be tested vs  $H_1: \text{ORR} > 50\%$

using a one-sided test with  $\alpha=0.05$  based on Simon's optimal two-stage design ([Simon 1989](#)). If 45 or more responses are seen in 105 total patients (estimated ORR of 42.9%), then  $H_0$  will be rejected and the trial declared positive.

Stage 1 will enroll 43 patients. If the study is terminated early at the end of Stage 1 (16 or fewer responses among 43 patients enrolled to Stage 1), then the study will be considered to have failed to reject  $H_0$ . See [Section 2.11](#) for further details of the stopping criteria for futility. Stage 2 will include an additional 62 patients. The primary analysis will occur when all 105 patients have completed 6 cycles of treatment or discontinued treatment earlier.

The ORR will be estimated and the 90% and 95% Clopper-Pearson (Clopper and Pearson 1934) confidence intervals (CIs) will be provided. The uniformly minimum variance unbiased estimator (UMVUE) and the 90% two-stage CI (Atkinson and Brown 1985) will also be presented. Refer to Section 4.6.4 for additional details.

Clopper-Pearson confidence intervals will be used since the confidence limits based on the normal approximation are not bounded by the  $[0, 1]$  interval, meaning that for rates close to 0 or 1, the upper limit of the normal approximation interval for the proportion could exceed 1 or the lower limit could be negative. The 90% two-stage CI will be presented to correspond to the Simon two-stage p-value.

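### The SAP names a Simon two-stage p-value but specifies only a single-stage one, and it writes H1 as ORR > 50% where the protocol tests ORR > 35%

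*SAP*

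**What the plan says.** **The p-value.** SAP 2.7.2 bases the primary test on Simon's optimal two-stage design at one-sided alpha 0.05. The decision is a count: "If 45 or more responses are seen in 105 total patients (estimated ORR of 42.9"%), H0 is rejected and the trial is positive. Stage 1 has 43 patients and stops for futility at 16 or fewer responses; Stage 2 adds 62. After listing the estimates and intervals, 2.7.2 says "Refer to Section 4.6.4 for additional details". Its next paragraph adds: "The 90% two-stage CI will be presented to correspond to the Simon two-stage p-value". Section 4.6.4, whose title covers both the confidence interval and the p-value for the response rate, describes a PROC FREQ call that produces a "two-sided Pearson-Clopper CI and exact one-sided p-value for ttle hypothesis test" against 0.35. It gives no other p-value.

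**The alternative.** Protocol 10.4.2 sets H0 as ORR of 35% or less and says "an alternative hypothesis of $ORR > 35\%$ will be tested using a one-sided test". The 50% figure enters as the target, and in protocol 10.8 as the value for power: "if the true ORR is 50% (under the alternative hypothesis"). SAP 2.7.2 writes H1 as ORR > 50%. The only row of SAP Table 3-1 that cites protocol Section 10.4 concerns confidence levels.

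Of SAP Section 2, the document says: "This section and its subsections will be imported to section 9.7 of the CSR after the analyses have been conducted".

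**The concern.** The PROC FREQ call takes the total sample, the number of responders and the null proportion. It has no input for the Stage 1 size, the futility bound or the Stage 2 size, so it cannot produce the p-value that 2.7.2 names. No other part of the SAP gives a method for it. SAP 2.2 cites an earlier analysis plan, but only for the per-protocol set definition. A programmer following 4.6.4 would report a single-stage p-value beside a two-stage decision rule and a two-stage interval, and at the boundary these disagree.

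With H0 at 35% or less and H1 above 50%, response rates above 35% and up to 50% belong to neither hypothesis. The declared success at 42.9% lies in that gap. Rejecting H0 there supports ORR > 35%; it cannot support ORR > 50%. Because Section 2 is to be carried into the study report, the wording would go with it.

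Three things are not at issue. The Clopper-Pearson intervals are planned by protocol 10.4.2 itself ("The ORR will be estimated and the 90% exact confidence interval (CI) will be provided"). SAP 2.7.2 does name the UMVUE and the two-stage interval. SAP 2.9 follows the 50% design alternative of protocol 10.8.

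**Working it through.** **Inputs** (SAP 2.7.2 and 2.9; protocol 10.4.2 and 10.8): p0 = 0.35; n1 = 43, continue only with at least 17 responses; n2 = 62, N = 105; success at 45 or more.

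**Step 1: reproduce the plan's table.** The success probability at true rate p is the sum over x1 = 17 to 43 of P(X1 = x1 | 43, p) × P(X2 ≥ 45 − x1 | 62, p). At 35, 40, 45 and 50% this gives 0.0487, 0.2678, 0.6418 and 0.9000. The probabilities of stopping at Stage 1 are 0.6828, 0.4178, 0.1916 and 0.0631. Both rows match SAP Table 2-3 to three decimals.

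**Step 2: the two p-values for r responses in 105.**
- Single-stage (4.6.4): P(X ≥ r | 105, 0.35).
- Two-stage: the sum over x1 = 17 to 43 of P(X1 = x1 | 43, 0.35) × P(X2 ≥ r − x1 | 62, 0.35).

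| r of 105 | Single-stage p | Two-stage p |
|---|---|---|
| 44 | 0.0848 | 0.0684 |
| 45 | 0.0579 | 0.0487 |
| 46 | 0.0382 | 0.0334 |
| 50 | 0.0052 | 0.0050 |

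At 45 the difference, 0.0579 − 0.0487 = 0.0092, is the probability of paths that reach 45 in total after 16 or fewer responses in Stage 1. The design does not allow those paths. The 45/105 rule meets alpha 0.05 only because of the Stage 1 stop.

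**Step 3: 90% intervals at 45/105.** Clopper-Pearson: 34.67% to 51.35%. Two-stage: 35.06% to 52.63%, found by inverting the two-stage tails with Stage 1 stops ranked below every continuing outcome (an assumption). On that ordering the two-stage interval excludes 35%, by 0.06 points, and the Clopper-Pearson interval does not.

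**Step 4: how likely the conflict is.** P(pass Stage 1 and total exactly 45) is 0.0153, 0.0513, 0.0555, 0.0209 and 0.0001 at true rates of 35, 40, 45, 50 and 60%.

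**Step 5: if the 4.6.4 p-value were read as the test.** Success would start at 46. Alpha would be 0.0487 − 0.0153 = 0.0334. Power would be 0.9000 − 0.0209 = 0.8791 at 50% and 0.6418 − 0.0555 = 0.5863 at 45%.

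**Step 6: the number actually treated.** The rationales for protocol Amendments 3 and 4 report 124 treated, and the FAS is everyone dosed. Assuming Stage 1 of 43 and Stage 2 of 124 − 43 = 81:

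| r of 124 | Single-stage p | Two-stage p |
|---|---|---|
| 52 | 0.0650 | 0.0513 |
| 53 | 0.0448 | 0.0367 |
| 54 | 0.0300 | 0.0254 |
| 62 | 0.00042 | 0.00041 |

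Both first fall below 0.05 at 53, so there is no count at which they conflict.

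**Step 7: the alternative.** Alpha is computed at 35% and power at 50%. The H1 wording enters neither calculation, so no boundary or error rate moves.

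**The case against.** The strongest reply is about consequence. Success is declared by a response count in both documents, and nothing tells the analyst to reject on the 4.6.4 p-value. The figures in Step 5 therefore describe a reading the SAP does not instruct. This SAP also covers the final analysis, and at 124 treated the two p-values agree. All of that stands, and it is why the point is minor.

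It can also be said that the pointer to 4.6.4 closes the paragraph on intervals, that the two-stage p-value is mentioned only in the next paragraph, and that the SAP never equates the two. On that reading 4.6.4 is incomplete and does not contradict 2.7.2. The gap remains either way: 4.6.4 is the section titled for the p-value, and the one that 2.7.2 names is specified nowhere.

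On H1, the protocol itself calls 50% the alternative hypothesis in 10.8, and 4.6.4 tests against 0.35, so the programmed test is unaffected. The inequality sign may also have been misread from the PDF. If it were ≥ 50%, it would still differ from the > 35% of protocol 10.4.2, and 42.9% would still lie outside it. The reply limits the harm to wording but does not make the wording right.

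**Conclusion.** Both items hold, at minor severity. The p-value in 4.6.4 is not the one 2.7.2 names, and at 45/105 it reads 0.0579 where the design gives 0.0487. The error is conservative and produces a contradictory report at that one count, which has probability 2.1% at a true ORR of 50% and 5.6% at 45%. With 124 treated there is no conflict, assuming stages of 43 and 81. The statement that the two-stage interval excludes 35% at 45/105 rests on the assumed ordering of outcomes. The H1 wording departs from the protocol without being declared and changes no figure, but it would put into the study report an alternative that a success at 42.9% cannot support.

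**What to change.** - **SAP 4.6.4:** replace the PROC FREQ p-value with the two-stage p-value of Step 2, evaluated at 0.35 with the actual stage sizes. Alternatively, keep the PROC FREQ value and label it single-stage and descriptive.
- **Clopper-Pearson intervals:** keep them as the protocol plans, identified as not adjusted for the two-stage design.
- **SAP 2.7.2:** restore H1 as ORR > 35%, and describe 50% as the design value for power.
- **SAP 2.9:** at most, clarify that 50% is the value at which power is computed, as in protocol 10.8.

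The cost is a few lines of SAP text and a short program, with no effect on data or conduct.

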## 4.7 Safety evaluations

The text below gives more detailed instructions and rules needed for programming of the analyses described in [Section 2.8.2](#).

### 4.7.1 Multiple assessments within post-baseline visits

For all analyses regarding abnormal assessments or analyses based on worst post-baseline value (laboratory, ECGs, vital signs, ECOG performance status), **all** post-baseline values will be included (scheduled, unscheduled, repeat). All unscheduled and repeat measurements will be included in listings.

#### Laboratory data

For laboratory data, assessments can be collected from both local and central laboratory on the same date. For shift tables using CTC grades to compare baseline to the worst post-baseline value, the assessment with worst post-baseline value is used for analyses irrespective of the source. For LFT summaries, where concurrent measurements are used in the calculation of number and percentage of patients with worst post-baseline values, the assessment with worst post-baseline value is used (since worst values are based on the largest ratio of lab value to its ULN for each patient) although the worst values for the different parameters may be coming from different laboratories.

#### ECGs

For all patients, 3 ECGs are targeted to be measured at the protocol-defined (nominal) time-points. If a patient has more than one measurement at a specific time point, the average of *all* available measurements associated with the nominal time point will be used for the analyses.

### 4.7.2 Baseline

As defined in [Section 2.8.2](#), the last available assessment before or on the date of start of study drug is defined as "baseline" value or "baseline" assessment.

#### Laboratory data

If both central and local laboratory assessments were performed on the same date and corresponding to the baseline assessment date, then the central laboratory assessment will be used for the calculation of baseline.

## ECGs

Baseline for ECG analysis is defined as the average of all available ECG measurements associated with the baseline assessment date. Study day 1 scheduled pre-dose ECGs will be considered to have been obtained prior to study drug administration if dosing time is missing.

If a scheduled pre-dose measurement actually occurred post-dose, then the corresponding measurement will be treated and analyzed similar to an unscheduled post-dose measurement.

### 4.8 Handling of missing or partial dates

For patients not known to have died prior to the cut-off date:

- All events with start date before or on the cut-off date, and with end date missing or after the cut-off date will be reported as "continuing at the cut-off date".
- This approach applies, in particular, to AEs and concomitant medication reports. For these events, the end date will not be imputed and therefore will not appear in the listings.

For patients known to have died prior to or on the cut-off date:

- All events with start date before or on the cut-off date, and with end date missing or after the cut-off date will have the end date imputed to the death date.
- This approach applies, in particular, to AEs and concomitant medication reports. For these events, the imputed end date will not appear in the listings.

If imputation of an end date is required for a specific analysis (e.g. for a dose administration record with missing end date or last date of study drug after the cut-off date), the end date will be imputed to the cut-off date for the purpose of calculating duration of exposure to study drug and dose intensity. The imputed date will be displayed and flagged in the listings.

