## 1 Introduction

This SAP describes the planned statistical methods for the final analysis for study LDK378A2203.

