### 2.1 Data analysis

Data will be analyzed by Novartis Oncology Biostatistics and programming personnel according to the data analysis section 10 of the LDK378A2203 protocol. Important information is given in the following sections and details are provided, as applicable, in Section 4 from which Appendix 16.1.9 of the CSR will be extracted.

SAS® version 9.4 (or later version if available at time of database lock) will be used in all analyses.

Data from all patients who signed informed consent in centers that participate in this study will be used in the analysis; due to expected small size of enrollment at individual centers, no center effect will be assessed. Each analysis will use all data in the database up to the analysis cutoff date, determined prior to database lock.

As described in Section 1.1 this study has a Simon two-stage design. If the study stops at the end of Stage 1 (see Section 2.11), the data available will be summarized in an abbreviated CSR. Otherwise, the analysis cut-off date for the primary analysis of study data will be established once all patients have either completed at least six treatment cycles, i.e., 168 days (1 cycle = 28 days), or discontinued study drug earlier. The data will be summarized in the primary CSR. Following the primary analysis time point, the study will remain open. Patients still being followed on the study will continue as per the schedule of assessments.

The analysis cutoff date for the final analysis of study data will be 22-Jan-2018 corresponding to last patient last visit date.

[Section 4.1](#) provides further details regarding data to be included in the analyses.

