### Date of first/last administration of study drug

The date of first administration of study drug is defined as the first date when a non-zero dose of study drug was administered and recorded on the Dosage Administration Record (DAR) eCRF. For the sake of simplicity, the date of first administration of study drug will also be referred to as start date of study drug.

The date of last administration of study drug is defined as the last date when a non-zero dose of study drug was administered and recorded on DAR eCRF. This date will also be referred to as last date of study drug.

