### Dose exposure and intensity

Definitions of duration of exposure, cumulative dose, average daily dose, actual dose intensity (DD), relative dose intensity (RDI), as well as intermediate calculations, include:

- Duration of exposure (days): last date of study drug - first date of study drug + 1 (periods of interruption are not excluded)
- Cumulative dose (mg): total dose of study drug taken by a patient in the study
- Number of dosing days (days): duration of exposure - number of zero dose days
- Average daily dose (mg/day): cumulative dose (mg) / number of dosing days (days)
- DI (mg/day): cumulative dose (mg) / duration of exposure (days)
- RDI (%):  $100 \times [\text{DI (mg/day)} / \text{planned dose (750 mg)}]$

Note: given the planned LDK378 dose of 750mg/day, the planned dose intensity can be calculated as  $\text{PDI (mg/day)} = \text{cumulative planned dose (mg)} / \text{Duration of exposure (days)}$ , where cumulative planned dose (mg) = Protocol planned dose of 750 (mg) \* Duration of exposure. RDI (%) which is calculated as  $100 * \text{DI} / \text{PDI}$  can be simplified as shown above.

Duration of study exposure to study drug, cumulative dose, average daily dose, DI and RDI will be summarized. In addition, the duration of exposure to study drug will be categorized into time intervals; frequency counts and percentages of patients with exposure in each time interval will be presented. Frequency counts and percentages of patients who have dose changes, reductions or interruptions, and the corresponding reasons, will be summarized.

Listings of all doses of the study drug along with dose change/interruption reasons will be produced.

[Section 4.5](#) provides further details on the definition of dose changes and interruptions.

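### A missing dosing end date is set to the final cut-off date without limiting this to patients still on treatment, so time off drug can be counted as exposure

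*SAP*

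**What the plan says.** The SAP covers one analysis: "This SAP describes the planned statistical methods for the final analysis for study LDK378A2203". SAP 2.1 fixes its cut-off: "The analysis cutoff date for the final analysis of study data will be 22-Jan-2018 corresponding to last patient last visit date".

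SAP 2.6 takes the last administration as the "last date when a non-zero dose of study drug was administered and recorded on DAR eCRF". It then defines exposure as "Duration of exposure (days): last date of study drug - first date of study drug + 1", with interruptions left in. Dose intensity is cumulative dose divided by that duration, and relative dose intensity (RDI) compares the result with 750 mg. The number of dosing days, and so the average daily dose, is derived from the same duration.

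SAP 4.8 first handles end dates by survival status. For patients not known to have died, events with no end date are reported as continuing. For patients known to have died, such events "will have the end date imputed to the death date". Both bullets refer to all events and name AEs and concomitant medications as particular cases.

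A separate sentence follows for analyses that need an end date, for example "for a dose administration record with missing end date or last date of study drug after the cut-off date". In those cases "the end date will be imputed to the cut-off date for the purpose of calculating duration of exposure to study drug and dose intensity", and the imputed date is displayed and flagged in the listings.

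**The concern.** The sentence treats two different situations alike. When the last dose falls after the cut-off, truncating at the cut-off is correct. When the end date is missing, the cut-off is correct only if the patient was taking drug up to that day. For a patient who had stopped, every day from the true last dose to 22-Jan-2018 is counted as exposure.

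Nothing in SAP 2.6, 4.5 or 4.8 caps the imputed date, although a better date is collected. Protocol 7.1.4.1 has the site record the date and reason for stopping on the End of Treatment page. The SAP already uses that page for disposition (2.5) and for the last contact date (4.3). SAP 2.8.2 separates discontinued from ongoing patients when it defines the on-treatment period. The dosing sentence in 4.8 makes no such distinction.

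At stake are the descriptive summaries of duration of exposure and the dose measures that divide by it.

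**Working it through.** The plan states no figure that depends on this rule, so there is none to reproduce. The check is date arithmetic with the SAP's own formulas.

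**Inputs from the documents**
- Cut-off: 22-Jan-2018 (SAP 2.1).
- Duration = last date − first date + 1; DI = cumulative dose / duration; RDI = 100 × DI / 750 (SAP 2.6).
- One month = 30.4375 days (SAP 4.4).
- Patients treated: 124 (Protocol, Amendment 4 rationale).
- Six cycles = 168 days (SAP 2.1).

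**Assumptions, not in the documents**
- First dose between 1-Jul-2013 and 1-Jul-2014.
- True exposure of an affected patient between 28 and 730 days.

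**Step 1: duration and excess.** Imputed duration is 22-Jan-2018 − first dose + 1, whatever the true stop date. Excess is imputed minus true duration.

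| Assumed first dose | Imputed duration | Excess if true = 28 d | Excess if true = 168 d | Excess if true = 730 d |
|---|---|---|---|---|
| 1-Jul-2013 | 1667 d (54.8 mo) | 1639 d (53.8 mo) | 1499 d (49.2 mo) | 937 d (30.8 mo) |
| 1-Jan-2014 | 1483 d (48.7 mo) | 1455 d (47.8 mo) | 1315 d (43.2 mo) | 753 d (24.7 mo) |
| 1-Jul-2014 | 1302 d (42.8 mo) | 1274 d (41.9 mo) | 1134 d (37.3 mo) | 572 d (18.8 mo) |

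The range is 572 to 1639 days, or about 19 to 54 months per affected patient.

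**Step 2: effect on the mean.** One affected patient moves the mean over 124 patients by 572 / 124 = 4.6 days to 1639 / 124 = 13.2 days.

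**Step 3: effect on dose intensity.** The SAP does not say whether cumulative dose is extended over the imputed days. Take a patient with 168 days at 750 mg, so a true cumulative dose of 168 × 750 = 126,000 mg and a true RDI of 100%.
- Not extended: RDI = 100 × 168 / 1667 = 10.1% for the earliest start, and 100 × 168 / 1302 = 12.9% for the latest.
- Extended at 750 mg: RDI stays at 100%, but cumulative dose becomes 750 × 1302 = 976,500 mg to 750 × 1667 = 1,250,250 mg.

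So either dose intensity is understated or cumulative dose is overstated, depending on a choice that the SAP leaves open.

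**Step 4: patients who died.** The death-date bullet covers all events with a missing end date, and its list of examples is not exclusive, so it can be read to include dosing records. The later sentence names dosing records and gives the cut-off. No wording ranks one above the other, and two programmers could implement it differently.

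**The case against.** The strongest defence is that this is a fallback of unknown, possibly nil, use. It operates only where an end date has to be imputed. Dosing dates are recorded on the eCRF, and SAP 4.8.1 (written for AEs) expects missing dates to be queried. No count of open dosing records is given. The rule is confined to exposure and dose intensity; the SAP does not say that it feeds ORR, DOR, PFS, OS or the 30-day safety window. An implausible imputed date would be visible in the listings. With one affected patient the median would barely move. All of this stands and keeps the point small.

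The defence also rules out some stronger readings that a reader might infer:

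- *Essentially every patient had stopped by last patient last visit, so the rule is nearly always wrong when it applies.* The documents do not say so. Protocol 4.3 lets the study end when ongoing patients can transfer to another study or support programme, and SAP 2.5 and 2.8.2 provide for patients still on treatment. For them the cut-off is the right date.
- *The dosing sentence overrides the death-date bullet, so exposure runs on after death.* No override is stated; this is an unreconciled conflict.
- *One affected patient would set the reported maximum.* The imputed value is the time from first dose to cut-off, so a patient who started earlier and was genuinely treated to the cut-off would exceed it.
- *The phase I median exposure of 26.9 weeks shows how far out the imputed values would be.* That median comes from another study, at its own cut-off, while that study was still ongoing.

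What the defence does not answer is the living patient who stopped before the cut-off and whose record is open. No competing rule applies, and the stated rule gives a wrong value.

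**Conclusion.** The point holds as a minor defect in a stated rule. As written, SAP 4.8 counts time off drug as exposure for any patient who discontinued before 22-Jan-2018 and whose dosing record still lacks an end date at lock. For patients who died, the section gives two targets without reconciling them. The per-patient excess and the shift in the mean rest on the assumed start dates and true exposures; an earlier start or shorter true exposure would enlarge them, and the reverse would shrink them. The total effect cannot be sized because the number of affected records is not given. Efficacy conclusions are not affected.

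**What to change.** Replace the dosing sentence in SAP 4.8 with a rule that takes the earliest available of three dates: the cut-off date, the date of stopping treatment on the End of Treatment page, and the date of death. This leaves the cut-off in place where it is right, namely for a last dose after the cut-off and for a patient with no End of Treatment page and no recorded death. It also removes the conflict with the death-date bullet.

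Add one sentence stating whether cumulative dose is extended over the imputed days and, if so, at what recorded dose level, so that dose intensity uses a matching numerator and denominator. Report the number of imputed dosing end dates as a footnote to the exposure table.

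The cost is two sentences in the SAP and a minimum function in the program. All the dates needed are already on the eCRF.
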